### **8.3 Interim Analysis**

No formal interim analysis is planned.

### **8.4 Safety Analyses**

Adverse events will be coded to system organ class and preferred terms using the Medical Dictionary for Regulatory Activities (MedDRA, Version 20 or higher).

Frequency and percentage of subjects reporting treatment-emergent adverse events (TEAEs) will be tabulated for each treatment by preferred terms and further by severity and relationship to study device. In summaries of severity and relationship, subjects reporting more than one event in a treatment arm that are mapped to the same preferred term will be counted only once in that treatment arm under the strongest severity and relationship, respectively. In addition, visual related TEAEs will be summarized separately for each treatment by preferred term.

Assessment results of lip function, lip sensitivity, lip texture, lip firmness, lip symmetry, and lip movement/function will be summarized with frequency and percentage for each scheduled visit.

Safety analyses will be conducted using the ITT population.

### **8.5 Sample Size Determination**

For the PRO 2018-02 study, the primary variable is change from baseline to Month 3 in LFGS. The sample size was determined based on (1) both PN40082 and Restylane Silk having an equal mean value with a common standard deviation of 0.85 for change from baseline in LFGS, and (2) the non-inferiority limit of -0.50. The test:control ratio of 1:1 results in 126 (63:63) PP subjects at 90% power. Assuming 80% of randomized subjects meet the PP criteria, a total of 158 (79:79) subjects will be randomized to obtain 126 (63:63) PP subjects.

## **9 ETHICS**

### **9.1 Informed Consent**

The principles of informed consent, according to Food and Drug Administration (FDA) regulations and International Council on Harmonization (ICH) guidelines on GCP, will be followed. A copy of the proposed ICF must be submitted with the protocol to the IRB for approval.

The informed consent process must be conducted and the ICF must be signed before each subject undergoes any Visit 1 procedures that are performed solely for the purpose of determining eligibility for the study, in compliance with 21 CFR Part 50. Each subject's signed ICF must be kept on file by the investigator for inspection by regulatory authorities at any time. A copy of the signed ICF will be given to the subject. A notation will be made in the subject's medical record indicating the date and time informed consent was obtained.

### **9.2 Institutional Review Board (IRB)**

The study protocol and ICF must be approved in writing by an appropriate IRB as defined by FDA regulations and other applicable requirements prior to enrollment of any study subjects.

Any changes to the protocol or a change of investigator approved by the Sponsor must also be approved by the site's IRB and documentation of that approval provided to the Sponsor or designee. Records of the IRB review and approval of all documents pertaining to this study must be kept on file by the investigator and are subject to inspection by regulatory authorities during or after completion of the study. SAEs must also be reported to the IRB.

Periodic status reports must be submitted to the IRB at least annually, as well as notification of completion of the study and a final report within 1 month of study completion or termination. A copy of all reports submitted to the IRB must be sent to the Sponsor or designee.

The investigator will ensure that an IRB that complies with the requirements set forth in 21 CFR Part 56 will be responsible for the initial and continuing review and approval of the study.

### **9.3 Subject Confidentiality**

All subject data will be identified only by a subject identification number and subject initials. However, in compliance with federal guidelines regarding the monitoring of clinical studies and in fulfillment of his/her obligations to the Sponsor, the investigator must permit the study monitor, Sponsor representative or auditor, and/or FDA representative or other regulatory authority to review the portion of the subject's medical record that is directly related to the study. This shall include all study-relevant documentation including medical history to verify eligibility, admission/discharge summaries for hospital stays occurring while the subject is enrolled in the study, and autopsy reports if a death occurs during the study.

As part of the required content of informed consent, each subject must be informed that his or her medical chart may be reviewed by the Sponsor, the Sponsor's authorized representatives, FDA or other regulatory authority. If access to the medical record requires a separate waiver or authorization, it is the investigator's responsibility to obtain such permission from the subject in writing before the subject is entered into the study.

### **9.4 Study Registration**

The study will be registered by the Sponsor on an appropriate free public web site such as [clinicaltrials.gov](http://clinicaltrials.gov), which is a service of the United States National Institutes of Health.

## 10 DATA HANDLING AND RECORDKEEPING

### 10.1 Site Regulatory Documents Required for Initiation

The Sponsor or designee will receive the following documents prior to the initiation of the study:

- Completed, signed Form FDA 1572
- Current curricula vitae, signed and dated, for the principal investigator (PI) and co-investigators named on Form FDA 1572
- Current license(s) of the PI and co-investigators named on Form FDA 1572
- Documentation of IRB approval of the study protocol, investigator, and ICF
- Current IRB membership list
- A copy of the protocol signature page signed by the PI
- Original Non-disclosure Agreements for the PI and co-investigators named on Form FDA 1572
- Debarment Certification for the PI and co-investigators named on Form FDA 1572
- Financial Disclosure Statement for all individuals named on Form FDA 1572

### 10.2 Maintenance and Retention of Records

The study will be conducted according to GCP as outlined in ICH guidelines by the FDA. It is the responsibility of the investigator to maintain a comprehensive and centralized filing system of all relevant documentation. Investigators will be instructed to retain all study records required by the Sponsor and the regulations in a secure and safe facility with limited access. Regulations require retention for a period of at least 2 years after marketing approval and notification from the Sponsor. These regulatory documents should be retained for a longer period if required by local regulatory authorities.

These records include documents pertaining to the receipt and return of study device, IRB, informed consent, source documents, and final signed CRFs. No documents shall be transferred from the site or destroyed without first notifying the Sponsor.

#### 10.2.1 Case Report Forms (CRFs)

CRFs for individual subjects will be provided by the Sponsor or designee. CRFs must be legible and complete. CRFs for this study will be maintained in a study binder and data recorded on 2-part NCR paper. One copy will be kept by the investigator and the other copy will be collected by the study monitor. All forms should be completed using a black ballpoint pen. Errors should be lined out, *but not obliterated*, and the correction inserted, initialed, and dated by designated study personnel. Further data corrections will be performed on special “data correction forms” (DCFs) that will be provided to the investigator in case of erroneous or unclear data. The investigator will make the correction on the DCF and sign the DCF. The original will be sent to the study monitor and a copy retained with the CRFs.

A CRF must be completed and signed by the investigator for each subject enrolled, including those withdrawn from the study for any reason. The reason for withdrawal must be noted on a subject’s study termination form.

CRFs must be kept current to reflect the subject’s status at each phase during the course of the study. Subjects are not to be identified on CRFs by name; appropriately coded identification and the subject’s initials must be used. The investigator must keep a separate log of the subjects’ names and addresses.

Source documents such as the clinic chart are to be maintained separately from the CRF to allow data verification. Because of the potential for errors, inaccuracies, and illegibility in transcribing data onto

CRFs, originals of laboratory and other test results must be kept on file with the subject's CRF. CRFs, source documents, and copies of test results must be available at all times for inspection by the study monitor. The following should also be available for review:

- Subject Screening Log, which should reflect the reason any subject screened for the study was found to be ineligible
- Delegation of Authority Log, which will list all site personnel with their responsibilities as delegated by the PI and their signatures. This log will be maintained at the site throughout the study
- Monitoring Log, which will list the date and purpose of all monitoring visits by the Sponsor or designee
- Enrollment Log, which will list subject initials and start and end dates for all enrolled subjects
- Product Inventory/Packing Slip, which will list the total amount of study device shipped to the site and received and signed for by the investigator
- Study Device Dispensing Log, which will list the lot number and total amount of study device used for each subject
- ICF, which must be available for each subject and be verified for proper documentation
- All correspondence

### 10.2.2 Primary Source Documents

The investigator must maintain primary source documents supporting significant data for each subject's medical notes. These documents, which are considered "source data," should include documentation of:

- Demographic information
- Evidence supporting the indication for which the subject is being studied
- General information supporting the subject's participation in the study
- General history and physical findings
- Hospitalization or Emergency Room records (if applicable)
- Each study visit by date, including any relevant findings/notes by the investigator(s), occurrence (or lack) of AEs, and changes in medication usage
- Any additional visits during the study
- Any relevant telephone conversations with the subject regarding the study or possible AEs
- An original, signed ICF for study participation

The investigator must also retain all subject-specific printouts/reports of tests and procedures performed as a requirement of the study. During monitoring visits the monitor will validate CRF entries against these data sources.

### 10.3 Study Monitoring

The Sponsor or designee will be responsible for monitoring the study according to GCP and applicable regulations. The study will be monitored by a Clinical Research Associate (CRA) in compliance with GCP, ICH guidelines, and applicable regulations. The investigator will be visited by a CRA prior to the study and at regular intervals during the course of the study. These visits are to verify adherence to the protocol. The CRA will review the ICFs and verify CRF entries by comparing them with the source documents (hospital/clinic/office records) that will be made available for this purpose. The CRA will review the maintenance of regulatory documentation and product accountability. The monitor will review the progress of the study with the investigator and other site personnel on a regular basis. CRFs may be collected during these visits. At the end of the study, a closeout monitoring visit will be

performed. Monitoring visits will be arranged with site personnel in advance at a mutually acceptable time. Sufficient time must be allowed by the site personnel for the monitoring of CRFs and relevant source documents. The coordinator and/or investigator should be available to answer questions or resolve data clarifications. Adequate time and space for these visits should be made available by the investigator and study staff.

#### **10.4 Audits and Inspections**

During the course of the study and/or after it has been completed, 1 or more sites may be audited by authorized representatives of the Sponsor. The purpose of the audit is to determine whether or not the study is being conducted and monitored in compliance with recognized GCP/ICH guidelines and regulations.

Additionally, the study may be inspected by regulatory authorities. These inspections may take place at any time during or after completion of the study and are based on local regulations.

#### **10.5 Modifications to the Protocol**

The procedures defined in the protocol and CRFs will be carefully reviewed to ensure that all parties involved with the study fully understand the protocol. To ensure the validity of the data, no deviations from the protocol (with minimal exceptions) may be made unless the issue is broad enough to warrant revision of the protocol. Such revisions must be submitted to and have documented approval from the Sponsor and IRB prior to implementation. The only circumstance in which an amendment may be initiated without prior IRB approval is to eliminate an apparent immediate hazard to a subject or subjects. In such a case, however, the investigator must notify the Sponsor immediately and the IRB within 5 working days after implementation.

#### **10.6 Completion of the Study**

The investigator is required to forward CRFs and all other relevant data and records to the Sponsor or designee. The investigator will complete and report (submission of CRFs) his/her study in satisfactory compliance with the protocol as soon as possible after the completion of the study.

The investigator must submit a final report to the IRB and the Sponsor within 1 month of study completion or early termination.

### **11 CONFIDENTIALITY, USE OF INFORMATION, AND PUBLICATION**

All information related to this study that is supplied by the Sponsor and not previously published is considered confidential information. This information includes but is not limited to data, materials (protocol, CRFs), equipment, experience (whether of a scientific, technical, engineering, operational, or commercial nature), designs, specifications, know-how, product uses, processes, formulae, costs, financial data, marketing plans and direct selling systems, customer lists, and technical and commercial information relating to customers or business projections used by the Sponsor in its business. Any data, inventions, or discoveries collected or developed as a result of this study are considered confidential. This confidential information shall remain the sole property of the Sponsor, shall not be disclosed to any unauthorized person or used in any unauthorized manner without written consent of the Sponsor, and shall not be used except in the performance of the study.

The information developed during the course of this study is also considered confidential and will be used by the Sponsor in the development of the study medication. The information may be disclosed as deemed necessary by the Sponsor. To allow the use of the information derived from this study, the investigator is obliged to provide the Sponsor with complete test results and all data developed in the study. The information obtained during this study may be made available to other investigators who are conducting similar studies.

The investigator shall not make any publication related to this study without the express written permission of the Sponsor. If the investigator wants to publish or present the results of this study, he or she agrees to provide the Sponsor with an abstract, manuscript, and/or presentation for review 60 days prior to submission for publication or presentation. The Sponsor retains the right to delete confidential information and to object to suggested publication/presentation and/or its timing (at the Sponsor's sole discretion).

### Filler First Aid Protocol (Wolters Kluwer Health, Inc, 2018)

#### **Materials that are needed on-site:**

- Hyaluronidase (Hyalenex)
- Aspirin 325mg
- Nitroglycerin paste

#### **Provide the following contacts to subjects and these contacts also posted on-site for easy reference:**

- Ophthalmologist “on call”
- Closest ER with stroke management capability with directions to ER

#### **Preparation:**

- The above materials should be gathered and labeled for emergency use only (to ensure they are available should an urgent situation arise).
- Staff should be educated regarding the urgent nature of such an event and the location of all materials and contact information.
- Investigators may wish to familiarize themselves with the retrobulbar injection technique via literature or on line training.

It is critical to recognize any intravascular events during injections and act quickly to maximize likelihood of reversal. As soon as an intravascular is recognized, **stop any further injections.**

#### **If a skin infarction is identified:**

- Apply nitroglycerin paste – apply liberally to the affected area and massage in gently, expect headache complaint from subject but do not withhold the treatment.
- Massage area to help promoted blood flow
- Dispense Aspirin 325 mg - Have patient chew this or the aspirin may be placed sublingually for maximum rapid absorption
- If blanching persists, consider infiltration with hyaluronidase
  - Infiltrate in the area where material was being injected – this may allow hyaluronidase to enter the same vessel that was inadvertently cannulated.
  - Infiltrate in the area of blanching or ischemia as well
  - Inject a minimum of 50 units into each area; investigators are free to use larger doses as they see fit.
  - Hyaluronidase may be repeated as needed.
- Hot Packs – Towels or gel packs warmed in a microwave can be applied to the area of decreased blood flow.
- Monitor the subject and the area of blanching ischemia. If blanching persists after 24 hours,– consider hyperbaric oxygen treatments.

**If signs/symptoms of visual changes, ophthalmoplegia, blindness, ocular pain (usually immediately)**

**occur:**

- Dispense Aspirin 325 mg - Have patient chew or place the tablet sublingually for maximum rapid absorption
- Massage the globe with repeated inward compression and release – this may free any embolic material
- Infiltration with hyaluronidase into area being corrected or augmented
- Have staff call ophthalmology: *Insert physician and cell phone number* or on-call ophthalmology at *nearest center with on-call ophthalmology*, and arrange transport
  - Bring hyaluronidase with the subject to the ophthalmologist – at least 300 units.
- If transport time to ophthalmology or ER is more than 60 minutes, consider performing retrobulbar hyaluronidase administration, 300-600 units at inferior, lateral orbital rim through orbital septum with 1-1.5 inch 27 gauge needle avoiding globe

After above measures, expedite to emergency room, the retina can tolerate approximately 90 minutes of ischemia until damage becomes permanent.

**If stroke symptoms are recognized:**

- Dispense Aspirin 325 mg - Have patient chew this or the aspirin may be placed sublingually for maximum rapid absorption
- Infiltration with hyaluronidase into area being corrected or augmented
- Call for transport to ER immediately
- Inform local stroke team during transport

## PN40082 INSTRUCTIONS FOR USE

### PN40082 Injectable Hyaluronic Acid Gel with 0.3% Lidocaine

Caution: Federal Law restricts this device to investigational use. This device is limited by Federal (or United States) law to investigational use

#### DESCRIPTION

PN40082 is a gel of hyaluronic acid generated by Streptococcus species of bacteria, chemically crosslinked with BDDE, stabilized and suspended in phosphate buffered saline at pH=7 with 0.3% lidocaine.

#### INDICATION

PN40082 is indicated for submucosal implantation for lip augmentation and dermal implantation for correction of perioral rhytids in patients over the age of 21.

#### CONTRAINDICATIONS

- *PN40082* is contraindicated for patients with severe allergies manifested by a history of anaphylaxis or history or presence of multiple severe allergies.
- *PN40082* contains trace amounts of gram positive bacterial proteins and is contraindicated for patients with a history of allergies to such material.
- *PN40082* is contraindicated for patients with bleeding disorders.
- *PN40082* is contraindicated for implantation in anatomical spaces other than the dermis or submucosal implantation for lip augmentation.
- *PN40082* should not be used in patients with previous hypersensitivity to local anesthetics of the amide type, such as lidocaine.

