### 7.3.2 Exclusion Criteria

Subjects who meet any of the following criteria will be excluded from the study:

1. Women who are pregnant, lactating, or planning a pregnancy
2. History of allergy, anaphylaxis or hypersensitivity to injectable hyaluronic acid products, local anesthetics of the amide type such as lidocaine, or to latex, or is planning to undergo desensitization therapy during the study
3. Has lip tattoos, piercings, facial hair, or scars that would interfere with visualization of the lips and perioral area for the effectiveness assessments
4. Has abnormal lip function, with inability to effectively sip water through a straw
5. Has abnormal lip sensation, with inability to feel a 0.4G monofilament or a cotton wisp at any site on the lip
6. Has moderate or severe abnormal lip asymmetry
7. Has any mass formation on the lip
8. Has dentures or any device covering all or part of the upper palate, and/or severe malocclusion or dentofacial or maxillofacial deformities as judged by the Treating Investigator. Subjects planning to undergo extensive dental procedures such as dental implants, multiple tooth extractions, or oral surgery should not participate. Minor dental procedures such as teeth cleaning and repair of caries are not exclusionary
9. Has undergone facial plastic surgery or received permanent facial implants (e.g., polymethylmethacrylate, silicone, polytetrafluoroethylene, polyacrylamide, lifting threads) anywhere in the face or neck, or is planning to be implanted with any of these products during the study
10. Has undergone semi-permanent dermal filler treatment (e.g., calcium hydroxylapatite, poly-L-lactic acid) in the lower face (below the orbital rim) within 12 months before enrollment or is planning to undergo such treatment during the study
11. Has undergone facial tissue augmentation with fat injections, botulinum toxin injections in the lower face (below the orbital rim), mesotherapy, or cosmetic procedures in the face or neck (e.g., face-lift, laser, photo-modulation, intense pulsed light, radio frequency, dermabrasion, moderate or greater depth chemical peel, microneedling, or other ablative procedures) within 9 months before enrollment or is planning to undergo any of these procedures during the study
12. Has used ANY lip filling agents within 12 months of study enrollment (hyaluronic acid products, collagen-based products, etc.)

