#### 7.4.2 Randomization

Subjects who satisfy all of the eligibility criteria will be randomized in a 1:1 ratio to treatment with PN40082 or Restylane Silk. Randomization will be performed according to a computer-generated randomization scheme that will be generated and maintained by an independent third party. A sealed copy of the randomization scheme should be retained at each site and should be available to regulatory authorities at the time of site inspection to allow for verification of the treatment identity for each subject.

A unique subject number will be assigned to each subject. Each site will receive the randomization scheme. Each eligible subject will be assigned a unique randomization code number in ascending order.

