**7.6.4 Significant Medical History/Demographic Information**

Medical history and demographic information will be obtained at Visit 1/Day 1. The medical history will include a complete review of all current diseases and their respective durations and treatments. Demographic information will include date of birth, sex at birth, race, ethnicity, and Fitzpatrick skin type (Table 1).

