## PRECAUTIONS

- *PN40082* is packaged for single use. Do not resterilize. Do not use if package is opened or damaged.
- The safety or effectiveness of *PN40082* for the treatment of anatomic regions other than lips or perioral rhytids has not been established in controlled clinical studies.
- As with all transcutaneous procedures, *PN40082* implantation carries a risk of infection. Standard precautions associated with injectable materials should be followed.
- The safety of *PN40082* for use during pregnancy, in breastfeeding females or in patients under 22 years has not been established, and these individuals are excluded from this study.
- Subjects with known susceptibility to keloid formation are excluded from this study. Formation of keloids may occur after dermal filler injections.
- Hyperpigmentation may occur after dermal filler injections. Subjects with known hyperpigmentation are excluded from this study.
- *PN40082* should be used with caution in patients on immunosuppressive therapy.
- Bruising or bleeding may occur at *PN40082* injection sites. Patients who have undergone therapy with thrombolytics, anticoagulants, or inhibitors of platelet aggregation in the 3 weeks preceding treatment with *PN40082* have not been studied.
- After use, syringes and needles should be handled as potential biohazards. Disposal should be in accordance with accepted medical practice and applicable local, state and federal requirements.
- The safety of *PN40082* with concomitant dermal therapies such as epilation, UV irradiation, or laser, mechanical or chemical peeling procedures has not been evaluated in controlled clinical trials.
- Patients should minimize exposure of the treated area to excessive sun, UV lamp exposure and extreme cold weather at least until any initial swelling and redness has resolved.
- If laser treatment, chemical peeling or any other procedure based on active dermal response is considered after treatment with *PN40082*, there is a possible risk of eliciting an inflammatory reaction at the implant site. This also applies if *PN40082* is administered before the skin has healed completely after such a procedure.
- Injection of *PN40082* into patients with a history of previous herpetic eruption may be associated with reactivation of the herpes.

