**CONTRAINDICATIONS**

- *Restylane Silk* is contraindicated for patients with severe allergies manifested by a history of anaphylaxis or history or presence of multiple severe allergies.
- *Restylane Silk* contains trace amounts of gram positive bacterial proteins, and is contraindicated for patients with a history of allergies to such material.
- *Restylane Silk* is contraindicated for patients with bleeding disorders.
- *Restylane Silk* is contraindicated for implantation in anatomical spaces other than the dermis or submucosal implantation for lip augmentation.
- *Restylane Silk* should not be used in patients with previous hypersensitivity to local anesthetics of the amide type, such as lidocaine.

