**WARNINGS**

- Defer use of *Restylane Silk* at specific sites in which an active inflammatory process (skin eruptions such as cysts, pimples, rashes, or hives) or infection is present until the process has been controlled.
- Injection site reactions (e.g., lip swelling, lip pain, and contusion) to *Restylane Silk* have been observed as consisting mainly of short-term minor or moderate inflammatory symptoms starting shortly after treatment, with an average of less than 18 days duration in the lips. In some cases delayed onset of these events has been observed with a range of 21 to 142 days after treatment. Most events with delayed onset resolved within 18 days. Injection site swelling appears to occur more frequently with the linear antegrade method of injection. Rare post-market *Restylane* reports of immediate post-injection reactions included extreme swelling of lips, the whole face and symptoms of hypersensitivity such as anaphylactic shock.
- Introduction of product into the vasculature may lead to embolization, occlusion of the vessels, ischemia, or infarction. Take extra care when injecting soft tissue fillers, for example inject the product slowly and apply the least amount of pressure necessary. Rare but serious adverse events associated with the *intravascular* injection of soft tissue fillers in the face have been reported and include temporary or permanent vision impairment, blindness, cerebral ischemia or cerebral hemorrhage, leading to stroke, skin necrosis, and damage to underlying facial structures. Immediately stop the injection if a patient exhibits any of the following symptoms, including changes in vision, signs of a stroke, blanching of the skin, or unusual pain during or shortly after the procedure. Patients should receive prompt medical attention and possibly

evaluation by an appropriate health care practitioner specialist should an intravascular injection occur.

- *Restylane Silk* must not be implanted into blood vessels. Localized superficial necrosis and scarring may occur after injection in or near vessels, such as in the lips, nose, or glabellar area. It is thought to result from the injury, obstruction, or compromise of blood vessels.
- Delayed onset inflammatory papules have been reported following the use of dermal fillers. Inflammatory papules that may occur rarely should be considered and treated as a soft tissue infection.

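### Two allergy contraindications in both device labels are missing from the exclusion criteria, so a subject contraindicated for both arms can be randomized

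*Protocol*

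**What the plan says.** The Contraindications sections of the two IFUs carry the same list. Each says that its device "is contraindicated for patients with severe allergies manifested by a history of anaphylaxis or history or presence of multiple severe allergies". On bacterial protein, the PN40082 IFU says the product "contains trace amounts of gram positive bacterial proteins and is contraindicated for patients with a history of allergies to such material", and the Restylane Silk IFU says that product "contains trace amounts of gram positive bacterial proteins, and is contraindicated for patients with a history of allergies to such material". The other three items are bleeding disorders, hypersensitivity to amide anesthetics, and implantation outside the intended tissue planes.

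Protocol 7.3.2 has 25 exclusions, and the synopsis repeats them. Only exclusion 2 concerns allergy: "History of allergy, anaphylaxis or hypersensitivity to injectable hyaluronic acid products, local anesthetics of the amide type such as lidocaine, or to latex". It ends with a clause on planned desensitization therapy.

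The route to randomization is Protocol 7.4.2: "Subjects who satisfy all of the eligibility criteria will be randomized in a 1:1 ratio to treatment with PN40082 or Restylane Silk". Section 7.4.5 likewise allows the device to be given to subjects who have consented and met all entry criteria.

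The Precautions section of the PN40082 IFU also states: "Subjects with known hyperpigmentation are excluded from this study".

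**The concern.** Entry criteria should be at least as strict as the contraindications of the devices being tested. Here they are looser, and for the same two conditions in both arms, so no allocation is safe for an affected subject.

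The hazard is documented. Both IFUs describe hyaluronic acid produced by *Streptococcus* bacteria, so the protein contraindication applies to each product. The Restylane Silk Warnings mention rare post-market Restylane reports that included "extreme swelling of lips, the whole face and symptoms of hypersensitivity such as anaphylactic shock". Its post-marketing section calls serious reports rare but lists hypersensitivity among the most common of them. The on-site emergency materials in Appendix 1 (hyaluronidase, aspirin, nitroglycerin paste) are meant for vascular events and include no treatment for anaphylaxis, which puts more weight on screening.

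The lapse would also leave no trace as an eligibility violation. With no criterion to breach, the subject would still satisfy the eligibility element of the mITT and PP definitions, and SAP Listing 16.2.2.2, with its 25 columns, has nowhere to show it.

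**Working it through.** The plan states no figure to reproduce. The check is a match of contraindications against criteria, followed by a scale calculation under an assumed prevalence.

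**Step 1. Match each IFU contraindication to the protocol.**

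| IFU contraindication (same in both) | Matching protocol text |
|---|---|
| Severe allergies shown by past anaphylaxis, or multiple severe allergies | None |
| Allergy to gram-positive bacterial proteins | None |
| Bleeding disorders | Exclusion 16 |
| Hypersensitivity to amide anesthetics | Exclusion 2 |
| Implantation outside dermis or submucosa | Injection technique, 7.4.3; not a subject characteristic |

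Setting aside the technique item leaves 5 − 1 = 4 patient-level contraindications. Two are covered, so 4 − 2 = 2 are not.

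**Step 2. Test exclusion 2 for partial coverage.** It removes subjects who reacted to an earlier hyaluronic acid filler, to an amide anesthetic or to latex, and anyone planning desensitization. It does not reach a filler-naive subject, or one whose anaphylaxis had another cause. Reading the word anaphylaxis in that criterion as free-standing goes against its grammar, and would still leave multiple severe allergies without anaphylaxis, and bacterial-protein allergy, uncovered.

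**Step 3. Look for another clause that closes the gap.**
- Section 7.9.6.3 cites the IFUs as the reference for adverse event expectedness, and 7.4.5 cites the Directions for Use for storage. Neither makes a contraindication an entry condition.
- On medical history, 7.6.4 says: "The medical history will include a complete review of all current diseases and their respective durations and treatments". A single past anaphylactic episode need not count as a current disease.
- Section 7.3 asks for healthy subjects, and 7.6.5 uses an examination to judge fitness to take part. Neither mentions allergy.

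**Step 4. Scale, under an assumption.** The documents give no prevalence. Let p be the share of otherwise eligible volunteers with such a history whom no other screen removes, and n = 158 (Protocol 8.5). The expected number is n × p, and P(at least one) = 1 − (1 − p)^n.

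| p (assumed) | Expected of 158 | P(at least one) |
|---|---|---|
| 0.1% | 0.16 | 14.6% |
| 0.5% | 0.79 | 54.7% |
| 1% | 1.58 | 79.6% |
| 2% | 3.16 | 95.9% |

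**Step 5. The related IFU statement.** The PN40082 Precautions make three statements that a group is excluded from this study. Pregnancy, breastfeeding and age under 22 match inclusion 1 and exclusion 1. Keloid susceptibility matches exclusion 20. Known hyperpigmentation matches nothing, so 1 of 3 is untrue of 7.3.2. This is a precaution for one device and separate from the allergy point.

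**The case against.** The best reply is that the IFUs are part of the protocol document. Section 7.6.1 makes the Treating Investigator responsible for giving the device in line with the protocol and other study instructions, so an investigator who injects someone listed under Contraindications is hardly following the document. Medical history can also be broader than current diseases: SAP Listing 16.2.4.3 has onset and stop dates, so resolved conditions may be recorded. Section 7.3.3 provides for withdrawing a subject whose safety is at risk. The Warnings passage on anaphylactic shock does not say that those patients had a prior allergy history. The assumed prevalence gives a chance of at least one affected subject anywhere from 15% to 96%, which says little about risk.

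Much of this is fair as to likelihood: a careful investigator may well turn such a volunteer away. But these protections rest on individual judgment or act only after randomization, and none is a written entry condition. The Investigator Agreement (Protocol section 13) is not in the copy available, so any duty it adds to follow labeling cannot be checked. The criticism of the prevalence range is accepted: the range illustrates scale, and the conclusion does not depend on it.

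**Conclusion.** The concern holds. In each IFU, 2 of 4 patient-level contraindications have no counterpart among the 25 exclusions, and randomization depends on the eligibility criteria alone. As written, the entry rules admit a subject for whom both devices are contraindicated, in an elective cosmetic procedure. This follows from the text and needs no assumption.

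The number of subjects affected is unknown. The figures of 0.16 to 3.2 expected subjects rest wholly on the assumed 0.1% to 2% and on no other screen removing them. The endpoint, sample size and analysis-set definitions are not affected. The hyperpigmentation mismatch is real but secondary. The change should be made for patient safety.

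**What to change.** Add two exclusions to Protocol 7.3.2 and to the synopsis, and to whatever eligibility form the sites use:

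1. Severe allergy shown by past anaphylaxis to any cause, or a past or current record of multiple severe allergies.
2. Any past allergy to gram-positive bacterial proteins.

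Add the matching columns to SAP Listing 16.2.2.2. For hyperpigmentation, either make it an exclusion or delete the sentence from the PN40082 IFU.

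The cost is low: two new criteria (three if hyperpigmentation is added), the same number of extra columns in one listing, and a slightly narrower eligible pool.
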